8.1.4.1. Reporting SAEs to Pfizer Safety

All SAEs occurring in a subject during the active collection period are reported to Pfizer Safety on the CT SAE Report Form.

SAEs occurring in a subject after the active collection period has ended are reported to Pfizer Safety if the investigator becomes aware of them; at a minimum, all SAEs that the investigator believes have at least a reasonable possibility of being related to investigational product must be reported to Pfizer Safety.

Follow up by the investigator continues throughout and after the active collection period and until the event or its sequelae resolve or stabilize at a level acceptable to the investigator, and Pfizer concurs with that assessment.

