8.1.4.2. Recording Non-serious AEs and SAEs on the CRF

During the active collection period, both non-serious AEs and SAEs are recorded on the CRF.

Follow-up by the investigator may be required until the event or its sequelae resolve or stabilize at a level acceptable to the investigator, and Pfizer concurs with that assessment.

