6.6.1. Adverse Events

The analyses of adverse events under the 3-tier approach described in [Section 3.5](#) is considered exploratory. There will be no adjustment for multiple comparisons or stratification factors in the analyses. For tier-1 events, the proportion of AEs observed in each group will be presented along with the point estimates and associated 95% confidence intervals of the risk difference, and p-value for dose comparison or regimen comparison using the exact methods proposed by Chan and Zhang (1999)² described in [Section 5.2.5](#). For tier-2 events, the proportion of AEs observed in each group will be presented along with the point estimates and associated 95% confidence intervals of the risk difference using the normal approximation for the difference in binomial proportions. In case of zero event rate for tier-2 events in any of group, the 95% confidence intervals will not be computed. AEs will be arranged in the output sorted in descending point estimate of the risk difference within system organ class. Tier 3 AEs will not be summarized separately, they are included

in the overall standard AE summary. Footnotes in the outputs will include the methods used to derive any p-values and confidence intervals as per Pfizer standards.

A listing of subjects with dose reduction due to PE risk factors will be provided.

Incidence Rates (IR) of Adverse Events of Special Interest will be provided. Confidence intervals (95%) will be computed using the exact Poisson method.

For regimen groups, IR will be calculated only for adverse event data for events of special interest only. The numerator will be the number of unique subjects with a treatment emergent event as defined above during the interval from the first dose in A3921288 study to last dose of tofacitinib + 28 days at risk period. The denominator of the incidence rate is person time accruing from the subject's first dose to last dose + 28 days, or to the date of the first event, whichever occurs earlier. For a subject who died, the time will be the minimum of (the date of the last dose + 28 days, or death date).

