For dose groups, IR will be calculated only for adverse events of special interest only. The numerator will be the number of unique subjects with a treatment emergent event as defined above during the interval from the first dose in A3921288 study to dose adjustment for dose escalated or dose reduced subjects otherwise to last dose + 28 days at risk period. The denominator of the incidence rate is person time accruing from the subject's first dose to day of dose escalation, or the first dose to day of dose reduction, or last dose + 28 days, or to the date of the first event, whichever occurs earlier. For a subject who died, the time will be the minimum of dose escalation day, dose reduction day, the day of the last dose + 28 days, or death day.

However, for mortality (death), malignancies (including NMSC), malignancies (excluding NMSC) and MACE related endpoints, all events regardless of their onset within 28 days or beyond after the last dose of tofacitinib will be included. The concept of 28 days is applied to subjects without events that discontinued or completed the study.

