7. INTERIM ANALYSES

7.1. Introduction

The data collected from this study will be analyzed at two time points.

The primary analysis will be performed to assess efficacy and safety when all subjects enrolled complete their Month 6 study visit (or drop out before Month 6 visit) and data are cleaned and locked. The primary analysis will include efficacy data up to Month 6 and safety data up to the data cutoff date, and will be performed only for dose group comparison. This will be considered as the primary completion date. The initial treatment assignments at baseline will remain double-blinded to the site and subject (i.e., Pfizer will not provide the individual subject treatment/randomization codes to the sites until the study is completed). The Pfizer study team will become unblinded at the time of the Month 6 primary analysis and will remain unblinded for the duration of the study. The Argus Safety Database will not be unblinded for the primary analysis. Results from the primary analysis may be shared with Regulatory Authorities and may be published for scientific presentation.

The final analysis will be performed when all subjects complete the study and the database is cleaned and locked. This secondary analysis will be performed for all efficacy endpoints and safety endpoints and for dose group, regimen group and the subgroup of subjects who escalate their dose from tofacitinib 5 mg BID back to tofacitinib 10 mg BID.

An external data monitoring committee (E-DMC) will be responsible for ongoing monitoring of the safety of subjects in the study according to the DMC charter. The recommendations made by the E-DMC to alter the conduct of the study will be forwarded to Pfizer for final decision. Pfizer will forward such decisions, which may include summaries of aggregate analyses of endpoint events and of safety data that are not endpoints, to regulatory authorities, as appropriate.

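### Incidence rates for death, malignancies and MACE count events after last dose + 28 days but stop event-free person-time there, so a captured late first event raises the rate, probably by a few percent

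*SAP*

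**What the plan says.** SAP 6.6.1 plans incidence rates with exact Poisson 95% intervals for adverse events of special interest. For most of these events the two parts of the rate match. In the regimen groups, events are counted to last dose + 28 days and person-time runs from "first dose to last dose + 28 days, or to the date of the first event, whichever occurs earlier". In the dose groups both parts also stop at dose escalation or reduction.

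For death, malignancies including NMSC, malignancies excluding NMSC and MACE, the section makes an exception to the count: "all events regardless of their onset within 28 days or beyond after the last dose of tofacitinib will be included". It then limits the cut-off: "The concept of 28 days is applied to subjects without events that discontinued or completed the study". Neither SAP 6.6.1 nor any other section plans a rate with matched time for these four endpoints.

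The end of the late period is only partly stated. SAP 7.1 has the Month 6 primary analysis use "safety data up to the data cutoff date". For the final analysis the bound has to be inferred from database lock.

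On collection, Protocol 8.1.4 sets active AE/SAE collection to at least 28 days after last dose. Protocol 8.1.4.2 states: "During the active collection period, both non-serious AEs and SAEs are recorded on the CRF". For later events, Protocol 8.1.4.1 states: "SAEs occurring in a subject after the active collection period has ended are reported to Pfizer Safety if the investigator becomes aware of them".

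**The concern.** A Poisson rate and its exact interval assume that events and time come from the same period at risk. Here a subject who has a cancer six months after stopping is counted, while a subject who goes the same six months without one contributes nothing for that time. The error has one direction: each captured late first event raises the point estimate and both limits.

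Capture after day 28 may also be incomplete, so the all-events rate can mix actively collected and later-reported events, and no planned output separates them. What is at stake is how the absolute rates of rare, serious events are read, alone or beside rates from other studies.

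**Working it through.** The plan states no incidence rate, person-time or expected event count, so there is no figure of its own to reproduce.

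**Inputs from the documents.** 138 enrolled at Amendment 2 (Protocol 9.1) and 1:1 allocation (Protocol 4.3) give n = 69 per arm. Maximum treatment is 42 months (Protocol 3), so T = 3.5 years. The cut-off is w = 28/365.25 = 0.0767 years (SAP 6.6.1).

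**Assumptions, not in the documents.** A share d = 10-40% discontinues evenly over 42 months. A share c = 10% or 25% of late first events is captured. The hazard is the same before and after day 28. Nobody changes dose, so the figures fit the regimen groups best; the dose groups, whose time stops at dose change, were not modelled.

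**Formulas.**
- Counted person-time: P = n[(1-d)T + dT/2] + nw
- Omitted late time to Month 42: F = n·d·(T/2 - w)
- Expected relative inflation: c·F/P
- With an assumed 6 further months per subject, F rises by 69 × 0.5 = 34.5 PY

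Example, d = 0.1: P = 69(3.15 + 0.175) + 69 × 0.0767 = 234.7 PY; F = 6.9 × 1.673 = 11.5 PY; at c = 25%, 0.25 × 11.5/234.7 = 1.2%.

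| d | P (PY) | F to Month 42 | Inflation, c = 10% / 25% | F with 6 more months | Inflation, c = 10% / 25% |
|---|---|---|---|---|---|
| 10% | 234.7 | 11.5 | 0.5% / 1.2% | 46.0 | 2.0% / 4.9% |
| 20% | 222.6 | 23.1 | 1.0% / 2.6% | 57.6 | 2.6% / 6.5% |
| 30% | 210.6 | 34.6 | 1.6% / 4.1% | 69.1 | 3.3% / 8.2% |
| 40% | 198.5 | 46.2 | 2.3% / 5.8% | 80.7 | 4.1% / 10.2% |

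With c = 0 the inflation is 0%.

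**How often a late event would appear.** Assume a true rate of 0.5-1 per 100 PY and c = 25%. Expected late events per arm and endpoint to Month 42 run from 0.005 × 11.5 × 0.25 = 0.014 to 0.01 × 46.2 × 0.25 = 0.115. The chance of none, exp(-E), is 99% to 89%. With the 6 extra months, the range is 0.005 × 46.0 × 0.25 = 0.058 to 0.01 × 80.7 × 0.25 = 0.202, and the chance of none is 94% to 82%.

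**Direction.** A late event raises the rate above its 28-day value unless that subject's own added time exceeds 1/rate, which is 200 PY at 0.5 and 100 PY at 1 per 100 PY. One subject cannot reach that.

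**The mismatch alone.** Take 69 subjects with an assumed mean exposure of 3 years: 69 × 3.0767 = 212.3 PY. Two first events fall inside the window and one falls 60 days after the cut-off.
- SAP rule, late subject's own time counted: 3/(212.3 + 60/365.25) = 3/212.5 = 1.41 per 100 PY (95% CI 0.29-4.13).
- Same three events, everyone's time extended by 60 days: 3/(212.3 + 69 × 60/365.25) = 3/223.6 = 1.34 per 100 PY.
- The SAP figure is 5.3% higher.
- Both parts ended at last dose + 28 days: 2/212.3 = 0.94 per 100 PY (0.11-3.40).

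**The case against.** The strongest defence is that the rule is deliberate and disclosed. The SAP introduces it as an exception, names its endpoints and says where the 28 days still apply. It keeps late deaths, cancers and MACE in view, which is cautious for safety. The rates are descriptive, and the inflation is small beside exact intervals as wide as 0.29-4.13. All of this stands. It is why the point is minor and why no event should be removed.

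It can also be said that late capture is better than it looks. The 28 days are a minimum. Protocol 8.1 requires all SAEs on the CRF. For subjects lost to follow-up, Protocol 6.4 has sites consult public records and, where a subject has died, seek the date and cause of death. So a reader who infers that nothing reliable arrives after day 28 goes too far. The documents support only that active collection is not guaranteed beyond that day and that late capture may be incomplete. Better capture makes the mismatch larger.

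Four stronger readings are tempting.
- *One late event can double a rate, so the bias is large.* With few events the rate does jump, but mostly because an event is counted at all. In the illustration the move from 0.94 to 1.34 would occur with matched time too; only 1.34 to 1.41 is the mismatch.
- *The dose comparison is biased.* SAP 6.6.1 attaches only confidence intervals to these rates. The tier-1 tests use proportions.
- *The all-events rule also overrides the dose-group cut at dose change.* The exception speaks only of time after last dose, and SAP 5.2.5 and 5.3.3 exclude dose-group data after a dose change.
- *The person-time rules for late deaths contradict each other materially.* The general sentences cap time: "For a subject who died, the time will be the minimum of (the date of the last dose + 28 days, or death date" for regimen groups and "the minimum of dose escalation day, dose reduction day, the day of the last dose + 28 days, or death day" for dose groups. The exception comes after them and confines the 28 days to event-free subjects, so it is naturally read as overriding them. For a death 100 days after last dose the two readings differ by (100 - 28)/365.25 = 0.20 PY, or 0.1% of 200 PY. This is a wording point only.

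**Conclusion.** The mismatch follows from the SAP's own text and holds as a minor point. The rates for death, malignancies and MACE, and their exact limits, are too high relative to matched time whenever a late first event is captured. Expected inflation is about 0.5-6% if late time ends at Month 42 and about 2-10% with 6 further months per subject. Both ranges rest on assumed discontinuation, assumed capture of 10-25% and a constant hazard. The direction is certain once a late event is captured; the percentages are not, because the documents supply none of the inputs that drive them. In most of the scenarios examined, an arm would have no late event at all for a given endpoint.

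**What to change.** In SAP 6.6.1, keep the all-events count and rate for the four endpoints. Beside it, report an incidence rate whose numerator and person-time both end at last dose + 28 days, or at dose change for the dose groups, consistent with SAP 5.3.3. List later events by group. Add to the method footnotes that the section already requires a note that the all-events rate has unmatched person-time.

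This supplements the all-events rate and does not repair it. Extending every subject's time past day 28 would match the periods, but it would credit time that is not actively followed and could understate the rate if late events are missed. The 28-day rate avoids both problems.

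One sentence could also state the person-time of a subject whose event or death falls after day 28. The cost is SAP wording plus one extra rate and one listing per endpoint. No new data are needed and no event leaves any planned output.

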7. INTERIM ANALYSES

7.1. Introduction

The data collected from this study will be analyzed at two time points.

The primary analysis will be performed to assess efficacy and safety when all subjects enrolled complete their Month 6 study visit (or drop out before Month 6 visit) and data are cleaned and locked. The primary analysis will include efficacy data up to Month 6 and safety data up to the data cutoff date, and will be performed only for dose group comparison. This will be considered as the primary completion date. The initial treatment assignments at baseline will remain double-blinded to the site and subject (i.e., Pfizer will not provide the individual subject treatment/randomization codes to the sites until the study is completed). The Pfizer study team will become unblinded at the time of the Month 6 primary analysis and will remain unblinded for the duration of the study. The Argus Safety Database will not be unblinded for the primary analysis. Results from the primary analysis may be shared with Regulatory Authorities and may be published for scientific presentation.

The final analysis will be performed when all subjects complete the study and the database is cleaned and locked. This secondary analysis will be performed for all efficacy endpoints and safety endpoints and for dose group, regimen group and the subgroup of subjects who escalate their dose from tofacitinib 5 mg BID back to tofacitinib 10 mg BID.

An external data monitoring committee (E-DMC) will be responsible for ongoing monitoring of the safety of subjects in the study according to the DMC charter. The recommendations made by the E-DMC to alter the conduct of the study will be forwarded to Pfizer for final decision. Pfizer will forward such decisions, which may include summaries of aggregate analyses of endpoint events and of safety data that are not endpoints, to regulatory authorities, as appropriate.

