9.4. Safety Analysis

The safety data will be summarized in accordance with Pfizer Data Standards based on the safety analysis set defined as all subjects who receive at least 1 dose of investigational product.

Summaries will be performed by dose group and dose regimen as defined in the efficacy sub-section.

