5.2.5. Analysis of Safety Data

Safety data will be summarized based on observed-case data by dose group, regimen group and the subgroup of subjects who are initially assigned to tofacitinib 5 mg BID and later are retreated with tofacitinib 10 mg BID. Missing data will not be imputed.

For dose groups, data collected after the dose escalation from tofacitinib 5 mg BID to 10 mg BID will not be included in the analyses.

For regimen group, data from subjects with dose escalation from tofacitinib 5 mg BID to 10 mg BID will be treated as it is.

For tier-1 adverse events, an unconditional exact method for risk difference proposed by Chan and Zhang (1999)² will be used to compare tofacitinib 10 mg BID to 5 mg BID (dose group), and tofacitinib fixed 10 mg BID to flexible 5 mg/10 mg BID (regimen group). P-values and 95% confidence intervals will be formed. For tier-2 events, the risk difference will be presented along with its 95% confidence interval using the normal approximation for the difference in binomial proportions. For tier-3 events, the risk difference will be reported.

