5.3.2. Safety Endpoints

Missing data for safety endpoints will not be imputed.

For dose groups, data collected after the dose escalation will not be included in the analyses. For regimen group, data from subjects with dose escalation back to tofacitinib 10 mg BID will be treated as it is.

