5.3.3. Method of Handling the Data after Dose Escalation or Dose Reduction

For this study, subjects may have a dose escalation to 10 mg BID due to flare or dose reduction to 5 mg BID due to PE risk factors. The data after the dose change for the dose group and regimen group are handled as follows.

- For Tofacitinib 10 mg BID dose group: For subjects with dose reduction due to PE risk factor, data collected after the dose reduction will not be included in the safety and efficacy analyses, and last observation carried forward (LOCF) will be used for binary and continuous efficacy endpoints. The subjects will be considered as censored at the dose reduction time for endpoint of time to loss of remission (flare).
- For Tofacitinib 5 mg BID dose group: data collected after the dose escalation (with or without dose reduction due to PE risk factor after the dose escalation) from tofacitinib 5 mg BID to 10 mg BID will not be included in the safety and efficacy analyses. The subjects will be treated as non-responders for any visit after the dose escalation visit for binary efficacy endpoints. For continuous efficacy endpoints, the data collected for any visit after the dose escalation visit will be considered as missing. For time to loss of remission (flare), the subject will be considered as having an event at the visit with a dose escalation if the event criteria are met or having a censored time at the visit with a dose escalation if the event criteria are not met.
- For Tofacitinib 10 mg BID regimen group: For subjects with dose reduction due to PE risk factor, data collected after the dose reduction will be included in the safety and efficacy analyses.

- For Tofacitinib 5 mg BID regimen group: Data collected after the dose escalation will be included in the analyses. For subjects with dose reduction due to PE risk factor after the dose escalation, data collected after the dose reduction will be included in the safety and efficacy analyses.

The following table provides some examples on how to handle the data after the dose escalation for flare and dose reduction for risk factors for PE:

Table 2 Examples on How to Handle Data After Dose Change

Examples	Dose group		Regimen group	
	Safety analysis	Efficacy analysis	Safety analysis	Efficacy analysis

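### At the primary analysis, adverse events after 5-to-10 mg escalation other than death, malignancy and MACE fall in no planned safety summary, and for those three the SAP is unclear

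*SAP*

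**What the plan says.** **Scope of the primary analysis.** SAP 7.1 limits efficacy to Month 6 but takes "safety data up to the data cutoff date, and will be performed only for dose group comparison". It adds: "Results from the primary analysis may be shared with Regulatory Authorities and may be published for scientific presentation". The final analysis, after all subjects finish, covers dose groups, regimen groups and the subgroup that escalated.

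**Dose-group safety rule.** SAP 5.3.2: "For dose groups, data collected after the dose escalation will not be included in the analyses". SAP 5.2.5 says the same: "For dose groups, data collected after the dose escalation from tofacitinib 5 mg BID to 10 mg BID will not be included in the analyses". SAP 5.3.3 states that data after escalation "from tofacitinib 5 mg BID to 10 mg BID will not be included in the safety and efficacy analyses", and Table 2 repeats it by example. For the regimen groups, these sections keep the post-escalation data.

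**Incidence rates.** In SAP 6.6.1 the dose-group window for events of special interest runs from first dose "to dose adjustment for dose escalated or dose reduced subjects otherwise to last dose + 28 days at risk period". The time at risk is cut in the same way after a death: "For a subject who died, the time will be the minimum of dose escalation day, dose reduction day". The next paragraph makes an exception for death, malignancies and MACE: all such events count, whether within or beyond 28 days of the last dose. It does not mention escalation.

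**Other scope statements.** Protocol 9.4: "Summaries will be performed by dose group and dose regimen as defined in the efficacy sub-section". SAP 6.6 asks for safety summaries by all three groupings. Neither names an analysis time point.

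**The concern.** Cutting dose-group data at escalation suits the primary objective, which is about subjects who stay on 5 mg: an event on 10 mg should not be charged to 5 mg. The difficulty is that SAP 7.1 makes this the only safety view in the first report while letting safety data run past Month 6 to the cutoff.

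Subjects who flared and went back to 10 mg are a group whose safety the second secondary objective sets out to evaluate. If the plan is followed as written, their later serious infections or herpes zoster events, for example, would not be in the summaries that may go to regulators or be published. Readers would take the adverse event counts as covering everyone treated up to the cutoff, and they would not. The gap is also one-sided, so it affects the comparison between arms as well as the totals.

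**Working it through.** **Step 1. Which grouping keeps the data, and when is it planned?**

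| Grouping | Safety data after escalation | Primary analysis (SAP 7.1) | Final analysis (SAP 7.1) |
|---|---|---|---|
| Dose group | Dropped (5.2.5, 5.3.2, 5.3.3, Table 2) | Yes | Yes |
| Regimen group | Kept (5.2.5, 5.3.2, 5.3.3, Table 2) | No | Yes |
| Re-treated subgroup | Kept (5.2.5) | No | Yes |

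The one grouping planned at the primary analysis is the one that drops the data.

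**Step 2. Can there be re-treatment time before the cutoff?** Yes. Protocol 5.11 allows escalation from the Month 1 visit. The primary analysis waits for the last subject's Month 6 visit. At Amendment 2 (19 June 2019), 138 subjects were enrolled and about 122 had passed Month 6 (Protocol 9.1): 122/138 = 88.4%, leaving 138 − 122 = 16 who had not. The cutoff must come later than that date, so most subjects had the opportunity for follow-up beyond Month 6.

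**Step 3. Does SAP 6.6.1 close the gap?** Not for most events. Dose-group incidence rates stop at escalation. The exception covers only death, malignancies and MACE, and two readings are open:
- Literal: all events count, including those after escalation. The numerator then includes events outside the time at risk, because the denominator still stops at escalation.
- Narrow: only the 28-day limit after the last dose is lifted, and the cut at escalation stays.

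The text does not decide between them.

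**Step 4. Direction.** Tier-1 and tier-2 comparisons use crude proportions (SAP 5.2.5, 6.6.1): subjects with the event divided by subjects in the arm. The cut removes from the numerator any 5 mg subject whose first such event follows escalation, and leaves the denominator unchanged. It can therefore only lower the 5 mg proportion. Subjects on 10 mg who flare remain on 10 mg (Protocol 5.11), and no rule cuts their data at flare. SAP 5.3.3 says the dose-reduction rules are not applied at the primary analysis. The 6.6.1 incidence-rate rule cuts at reduction without that exemption, so these two also need aligning.

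**Step 5. Size.** The plan gives no figure on this point. Its one design figure, a half width of about 16%, reproduces (1.96 × √(2 × 0.70 × 0.30/65) = 0.158) but plays no part here. As illustration only, take 138/2 = 69 subjects in the 5 mg arm (1:1 allocation). Let f be the share that escalates before the cutoff, t the mean years from escalation to cutoff, and r the serious events per 100 person-years. All three are assumptions.

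Person-years omitted = 69 × f × t; expected events E = person-years × r/100; chance of at least one = 1 − exp(−E).

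| f | t | r | Subjects | Person-years | E | Chance of at least one |
|---|---|---|---|---|---|---|
| 10% | 0.5 | 3 | 6.9 | 3.5 | 0.10 | 10% |
| 20% | 1.0 | 6 | 13.8 | 13.8 | 0.83 | 56% |
| 30% | 1.5 | 10 | 20.7 | 31.0 | 3.1 | 96% |

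Here r covers serious events of every type, so the number excluding death, malignancy and MACE would be somewhat smaller. The range runs from probably none to about three.

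**The case against.** The case on the other side has real force.

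- **Deaths, malignancies, MACE.** A reader might infer that deaths and malignancies on re-treatment appear nowhere in the first report, or that its death count must be too low. The documents do not support that. Read literally, the 6.6.1 exception includes them. What can be said is that the SAP is ambiguous.
- **SAP 6.6 and Protocol 9.4.** Both provide for regimen summaries without a time limit, and the restriction in 7.1 could be read as limiting the comparison, not descriptive tables. This is possible, but 7.1 is the specific text on timing and lists the other groupings only under the final analysis. The two sections need reconciling on either reading.
- **Deferral is planned.** Protocol 9.5 puts the final analyses for secondary objectives at study end. A reader might infer that the events are lost or unmonitored. They are not: the final analysis covers them, the E-DMC monitors safety throughout, and SAEs are reported to the sponsor under Protocol 8.1. This stands. However, Protocol 9.5 also makes safety part of the primary analysis without confining it to dose groups, and E-DMC review does not complete a published report.
- **Unseen standards.** Safety is summarised under sponsor data standards that are not in the documents and might call for listings of deaths and SAEs. That cannot be checked, and the plan itself does not mention such a listing.
- **Size.** A reader might take the 72.7% still in remission after 12 months on 5 mg (Protocol 1.2) to mean that about 27% would escalate. Those were different subjects and a different outcome: escalation here needs an endoscopically confirmed flare and is optional. The figure should not be used.

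**Conclusion.** The concern holds in a limited form. On the natural reading of SAP 7.1 with the dose-group rules, adverse events and SAEs after escalation and before the cutoff, other than death, malignancy and MACE, are in no planned summary of a primary analysis that may be published. Only the arm randomised to 5 mg is affected, and the effect on its crude proportions is downward. For the three excepted event types the SAP does not settle whether they are counted.

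This rests on letting 7.1 prevail over the undated statement in 6.6, and on no further output being required by standards outside the documents. The size is unknown; the illustration in the working rests wholly on assumed escalation, follow-up and event rates. The matter should be corrected before the primary analysis is reported, but it does not touch the primary efficacy result.

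**What to change.** 1. In SAP 7.1, keep primary-analysis efficacy by dose group only, and add regimen-group safety summaries by randomised arm with all data to the cutoff. At minimum, report deaths, SAEs, discontinuations due to adverse events, adjudicated events and events of special interest for all treated subjects regardless of escalation.
2. Reconcile SAP 7.1 with SAP 6.6 by stating which groupings are produced at which analysis.
3. In SAP 6.6.1, state whether the exception for death, malignancy and MACE overrides the cut at escalation and, if it does, what time at risk goes with it. Align the cut at dose reduction with the statement in SAP 5.3.3 in the same edit.
4. Footnote the dose-group safety tables to say that follow-up in the 5 mg arm stops at escalation.

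The cost is a few sentences and an earlier run of tables already planned for the final analysis. SAP 7.1 already has the study team unblinded at that point, and no new data are needed.
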